13 MEASUREMENT OF EFFECT

13.1 RESPONSE CRITERIA

13.1.1 Complete remission (CR) requires all of the following:

- o No evidence of leukemic cells by routine H/E stains of the peripheral blood and bone marrow. Minimal Residual Disease (MRD): CR with HCL evident in blood by flow cytometry (FACS) or in bone marrow by immunohistochemistry. One negative bone marrow biopsy is sufficient to confirm CR providing it is done after the normal blood counts qualify for at least 4 weeks.
- o No hepatomegaly, splenomegaly, or lymphadenopathy (not >2 cm in short axis) by physical examination and appropriate radiographic techniques. Adenopathy which persisted but became negative by biopsy would be consistent with CR.
- o Normal CBC as exhibited by: Neutrophils \geq 1,500/uL, Platelets \geq 100,000/uL, and Hemoglobin \geq 11.0 g/dL without transfusions or growth factors for at least 4 weeks. After this 4 week period the bone marrow biopsy and CT must be done to confirm CR.

13.1.2 Partial Response (PR) requires all of the following for a period of at least 4 weeks:

- The patient must have the following (if abnormal prior to treatment):
 - o \geq 50% decrease in hairy cell count from the pretreatment baseline value by flow cytometry. Flow cytometry will not prevent consideration of PR or determine relapse from PR if the HCL count by flow cytometry remains below 50 cells/mm³ and the patient qualifies for PR by other parameters.
 - o \geq 50% reduction in abnormal hepatosplenomegaly by CT or physical exam.
 - o No growth in lymphadenopathy. As HCL is not PET-avid, adenopathy which is stable is considered not measurable to determine PR, and would not contradict a PR proven by other criteria.
- and the following:
 - o Neutrophils \geq 1,500/uL or 50% improvement over baseline without growth factors for at least 4 weeks,
 - o Platelets \geq 100,000/uL or 50% improvement over baseline, &
 - o Hemoglobin \geq 11.0 g/dL or 50% improvement over baseline without transfusions or growth factors for at least 4 weeks. The baseline Hgb for patients who are transfusion dependent for red cells is assumed to be 6 g/dL.

13.1.3 Progressive disease (PD): Defined by at least one of the following compared to pretreatment:

- o \geq 25% increase in the sum of the products of the greatest perpendicular dimensions of at least two lymph nodes on two consecutive examinations at least

- 2 weeks apart (at least one node must be ≥ 2 cm) or appearance of new palpable lymph nodes,
- $\geq 25\%$ increase in the size of the liver and/or spleen as determined by measurement below the respective costal margin, or appearance of new palpable hepatomegaly or splenomegaly that was not previously present,
- $\geq 50\%$ increase in the number of circulating HCL cells by flow cytometry, and >50 cells/mm³.

13.1.4 Stable disease: (SD) will be characterized by not meeting any of the criteria outlined above.

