Objectives. The purpose of this study is to determine the activity of anti-Tac(Fv)-PE38 (LMB-2) in patients with CD25-expressing hairy cell leukemia (HCL). The primary endpoint of this trial is response rate.

Eligibility. Patients must have CD25+ HCL cells by flow cytometry, cytopenia or high circulating HCL count, prior treatment with or inability to receive BL22, prior treatment with cladribine, ECOG PS 0-2, at least 18 years old, ALT and AST grade 0-2, albumin grade 0-1, bilirubin \leq 2.2, creatinine \leq 1.4 or creatinine clearance \geq 50, lack of high levels of neutralizing antibodies, lack of anti-CD25 Mab therapy for 12 weeks and other systemic treatment for 4 weeks, no prior treatment with LMB-2, lack of other uncontrolled illness including 2nd malignancy, no HIV or hepatitis C positivity, no coumadin therapy, LVEF \geq 45%, DLCO \geq 55%, and FEV1 \geq 60%.

Design. Patients will receive LMB-2 at 40 μ g/Kg QOD x3 at intervals of at least 25 days for up to 6 cycles. Retreatment is permitted in the absence of neutralizing antibodies or progressive disease. Patients in CR may receive 2 consolidation cycles, or 4 consolidation cycles if CR is with minimal residual disease.

Dose level: LMB-2 40 μ g/Kg QOD x3

Expected Accrual: 5-10 patients/year, total of 25 evaluable patients

TABLE OF CONTENTS

PRÉCIS	2
TABLE OF CONTENTS	3
STATEMENT OF COMPLIANCE	5
1 OBJECTIVES	5
1.1 Primary	5
1.2 Secondary	5
2 BACKGROUND	5
2.1 Hairy Cell Leukemia (HCL).....	5
2.2 Salvage therapy for HCL.....	6
2.3 LMB-2 development	7
2.4 Rationale of Study Design.....	13
2.5 Dose Determination.....	14
3 ELIGIBILITY ASSESSMENT AND ENROLLMENT.....	14
3.1 ELIGIBILITY CRITERIA	14
3.2 Research Eligibility Evaluation	15
3.3 Inclusion of Women and Minorities.....	16
3.4 Recruitment Strategies	16
3.5 Participant Registration and Status Update Procedures	16
4 STUDY IMPLEMENTATION.....	16
4.1 Study Design	16
4.2 Drug Administration.....	17
4.3 Pharmacokinetic studies	19
4.4 On Study Evaluation	20
4.5 Cost and Compensation.....	21
4.6 Toxicity Criteria	22
4.7 Retreatment	22
4.8 Supportive Care	22
4.9 Criteria for Removal from Protocol Therapy and Off Study Criteria	23
4.10 Post Treatment Evaluation (off treatment but on study)	23
4.11 Off-study Criteria	23
4.12 Lost to Follow-up	24
5 HUMAN SUBJECTS PROTECTIONS	24
5.1 Rationale for Subject Selection	24
5.2 Participation of Children	24
5.3 Participation of Subjects Unable to Consent.....	24

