4.8 SUPPORTIVE CARE

- Allergic reaction will be treated acutely with antihistamines (including diphenhydramine, hydroxyzine, & ranitidine), fluids, bronchodilators, and/or epinephrine.
- Nausea and Vomiting: Patients who develop nausea will be treated with a serotonin 5-HT receptor inhibitor for at least 24 hours after their last episode of nausea. Other antiemetics such as prochlorperazine, metoclopramide, or lorazepam may be used in addition if necessary.
- Myalgias: Patients who develop myalgias may be given acetaminophen 650 to 1000 mg every 6 hours until 24 hours after completing the last dose of LMB-2. It may then be given as needed. Patients may receive NSAIDs or opioid analgesics if acetaminophen is inadequate.
- Vascular leak syndrome/Capillary leak syndrome: supportive care may include fluid and electrolyte management, diuresis, albumin, and cardiovascular support.
- Hypotension: Patients will be encouraged to increase oral fluid intake. In addition, for an orthostatic SBP change of >20 mm Hg and an absolute SBP of <100 mm Hg, an IVF bolus may be given as deemed clinically appropriate. Refractory hypotension may require treatment in the intensive care unit with pressors.
- Fever: Patients who develop temperatures >38.0° C may receive scheduled acetaminophen 650 to 1000 mg every 6 hours until 24 hours after completing the last dose of LMB-2. It may then be given as needed.
- Thrombocytopenia should be treated conservatively. In the absence of bleeding or a planned invasive procedure, platelet transfusions should only be given for a platelet count below 10,000. If invasive procedures are planned or the patient develops bleeding, platelet transfusions should be administered in accordance with standard of practice, usually maintaining a platelet count > 50,000/mm³.
- Symptomatic anemia should be treated with appropriate red blood cell support. Transfusion is recommended if the hemoglobin falls below 8g/dL. Recombinant erythropoietin may be also be used.

- Febrile Neutropenia is a life-threatening complication requiring hospitalization and urgent broad-spectrum antibiotics. Hematopoietic growth factors may be used if clinically indicated. Such cases will be evaluated individually to determine the toxicity grade. Neutropenia due to LMB-2 is not expected.

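### The PR platelet criterion in 13.1.2 carries no transfusion or growth-factor condition, so a platelet count held up by repeated transfusion could meet the platelet part of a PR counted in the primary endpoint

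*Combined protocol and SAP*

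**What the plan says.** The Précis states: "The primary endpoint of this trial is response rate". Section 15.2 counts CR and PR together in both decision rules: 3 or more of 10 to continue, and 6 or more of 17 to call the agent active.

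Section 13.1.2 opens with "Partial Response (PR) requires all of the following for a period of at least 4 weeks" and then sets the three blood counts on separate lines, each with a lower limit:

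- Neutrophils: "1,500/uL or 50% improvement over baseline without growth factors for at least 4 weeks".
- Platelets: "100,000/uL or 50% improvement over baseline", with no further condition.
- Hemoglobin: "11.0 g/dL or 50% improvement over baseline without transfusions or growth factors for at least 4 weeks".

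The section then adds: "The baseline Hgb for patients who are transfusion dependent for red cells is assumed to be 6 g/dL". No corresponding rule is given for platelets.

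For CR (13.1.1), neutrophils, platelets and hemoglobin stand in one sentence that ends "11.0 g/dL without transfusions or growth factors for at least 4 weeks".

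Section 4.8 permits platelet transfusion on study. Without bleeding or a planned invasive procedure, "platelet transfusions should only be given for a platelet count below 10,000". With either of these, the count is usually kept above 50,000. Section 3.1.1.2 makes platelets below 100,000/uL one of the indications for entry.

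**The concern.** Support conditions in 13.1.2 are written line by line, and the platelet line has none. A transfused count reflects donor platelets and not marrow recovery, which is presumably why the protocol excludes supported values for hemoglobin and, on the natural reading, for all three counts in CR. The relative arm of the platelet criterion is also easiest to reach, in absolute terms, for the patients with the lowest baselines, who are the most likely to be transfused.

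At stake is whether a given patient counts as a responder in a small two-stage trial. The decision thresholds are 3/10 and 6/17, and the design has little room between its actual type I error and the stated 0.10.

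**Working it through.** **1. The text.** The three PR count lines and the CR sentence compare as follows.

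| Count | PR (13.1.2) | CR (13.1.1, natural reading) |
|---|---|---|
| Neutrophils | no growth factors, 4 weeks | no transfusions or growth factors, 4 weeks |
| Platelets | no support condition | no transfusions or growth factors, 4 weeks |
| Hemoglobin | no transfusions or growth factors, 4 weeks | no transfusions or growth factors, 4 weeks |

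Sections 13.2 and 13.3 do not exclude transfused values. Section 13.3.1 allows isolated unacceptable CBC values, and values up to day 12 of each cycle, to be ignored when response duration is judged.

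**2. Where the relative threshold falls.** The requirement is 1.5 × baseline. A baseline of 10,000/uL needs 15,000/uL. A count held at 50,000/uL meets the requirement for any baseline up to 50,000 / 1.5 = 33,333/uL, provided that it is sustained.

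**3. The plan's own design figures.** Inputs from 15.2: n1 = 10, stop at 2 or fewer; n = 17, active at 6 or more; p0 = 0.20; p1 = 0.50; alpha = beta = 0.10.

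- Early termination = P(X ≤ 2 | n = 10, p = 0.20) = 0.678. The plan states 0.68.
- P(declare active | p) = Σ over x from 3 to 10 of P(X1 = x | 10, p) × P(X2 ≥ 6 − x | 7, p).
- At p = 0.20 this is 0.094. At p = 0.50 it is 0.904.

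The design reproduces and is sound as stated.

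**4. Sensitivity to miscounted PRs.** Let f be the share of true non-responders who are counted as PR. The documents give no value for f, so each value below is an assumption. At a true rate of 20%, the apparent rate is 0.20 + 0.80 × f, which goes into the formula in step 3.

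| Assumed f | Apparent rate | P(declare active) |
|---|---|---|
| 0 | 20.0% | 0.094 |
| 1% | 20.8% | 0.110 |
| 2% | 21.6% | 0.127 |
| 5% | 24.0% | 0.185 |
| 10% | 28.0% | 0.304 |

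Even f = 1% takes the error rate past 0.10, because the design starts at 0.094. This shows how sensitive the rule is to a miscounted responder. It does not show how often miscounting would happen.

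**The case against.** The strongest reply is that the route to a false PR is narrow, and most of that reply stands.

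- **Only one component is affected.** A reader might infer that transfusion alone can produce a primary-endpoint response. It cannot. PR also requires the neutrophil and hemoglobin criteria under their own conditions, no nodal growth and, where abnormal at baseline, reductions of at least 50% in hairy cell count and in enlarged liver or spleen. The exposed patient meets all of these and falls short on platelets alone.
- **Four weeks are required.** A reader might also infer that anyone with a baseline of 33,000 or less who is transfused above 50,000 qualifies. The documents do not support that: one post-transfusion value is not a PR. Support would have to be repeated, or the low values would have to fall within what 13.3.1 allows to be ignored.
- **Section 4.8 restricts transfusion.** Without bleeding or a procedure, it is reserved for counts below 10,000. For a baseline of 8,000, which needs 12,000, every such transfusion is prompted by a count that fails the PR threshold. The level above 50,000 applies only to bleeding or procedures.
- **The wording might reach back.** The hemoglobin clause could be read across the ampersand to include platelets. Separate lines, and a different condition on the neutrophil line, make this the weaker reading. If it was intended, the text is ambiguous and still needs the clause.

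The error rates in the working are not estimates, since nothing in the documents fixes f. What remains is that no provision excludes a transfused platelet count from PR.

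**Conclusion.** The omission is real and is not closed elsewhere in the protocol. A platelet count supported by repeated transfusion over the four-week period could satisfy the platelet component of a PR that enters the primary CR+PR rate, for a patient who meets every other PR criterion. Few patients are likely to be in that position.

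The size of any bias cannot be derived from the documents. Over an assumed miscounting range of 1% to 10% of true non-responders, the probability of declaring a 20% agent active runs from 0.110 to 0.304, against 0.094 by design. A reader might conclude from this that the Simon design is wrong or that its false-positive rate is in fact doubled. Neither follows: the design figures are correct, and the larger values rest entirely on the assumed f.

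The point merits correction because it concerns the definition of the primary endpoint and the remedy is cheap.

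**What to change.** In 13.1.2, add to the platelet line the condition that already closes the hemoglobin line: the count must be met with neither transfusions nor growth factors for at least four weeks. This brings the PR platelet criterion into line with PR hemoglobin and with CR.

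Apply the clause to all patients. Check any PR already assigned that relied on platelets against the transfusion records. If a case is affected, report the response count with and without it.

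Setting a platelet-dependent patient's baseline at the lowest pre-transfusion count should not be part of the change. It would lower the bar further: a nadir of 4,000 would need only 1.5 × 4,000 = 6,000.

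The cost is one clause and a review of transfusion dates, with the possibility that the observed response rate falls slightly. Sample size and decision thresholds stay as they are. Only the endpoint definition changes, not transfusion practice.

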4.4 ON STUDY EVALUATION

4.4.1 Prior to Each Cycle the following will be done:

- Staging will be completed prior to each cycle. This will include an interim history and physical examination with documentation of measurable disease, stage, and performance status. Physical examination should record the diameter, in two planes, of the largest palpable nodes in each of the following sites: cervical, axillary, supraclavicular, inguinal, and femoral. Physical examination should record liver and spleen size as determined by measurement below the respective costal margin.
- FACS analysis of the peripheral blood will be done.
- Laboratory evaluation to be done on or within 3 days prior to day 1 are: CBC/diff, acute care panel, hepatic panel, mineral panel, LDH, PT, PTT, urinalysis, fibrinogen, D-dimer, uric acid, amylase, lipase, CK, IgG, IgA, IgM, CRP, ferritin, haptoglobin, Beta-2 microglobulin and SPEP, 24 hour urine.
- ECG, CXR.

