4.9.1 Criteria for removal from protocol therapy

- Progression of disease during active treatment on study protocol.
- Grade III Allergic Reaction and grade II urticaria despite premedication.
- More than 2 dose reductions are required.
- Patient non-compliance or voluntary withdrawal.
- Patient's serum neutralizes $> 75\%$ of the activity of 1 $\mu\text{g}/\text{mL}$ of LMB-2.
- Grade IV toxicity other than hematologic and CPK.
- Grade IV hematologic toxicity lasting > 5 days.
- Grade IV CPK associated with any other DLT or not resolving to $<$ grade II within 2 weeks.

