13.2 MEASUREMENT OF RESPONSE

Assessment of clinical response will be made according to the guidelines as outlined above. The objective measures of response, such as bone marrow slides and CT scans, will be saved so that responses may be audited. Staging will include a CBC/differential, an interim history and physical examination with documentation of measurable disease, and performance status. Physical examination should record the diameter, in two planes, of the largest palpable nodes in each of the following sites: cervical, axillary, supraclavicular, inguinal, and femoral. Physical examination if relevant can record liver and spleen size as determined by measurement below the respective costal margin. A CT/MRI or U/S (in patients with an abnormal initial scan) will be done routinely after even cycle numbers (2, 4, 6, 8, 10) and will be done at other times if there is clinical evidence that the patient has had a PR, CR, or progressive disease.

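### Organ PR may be scored by CT or palpation with no rule for disagreement, and organ PD rests on an unrepeated palpated length in which the scan ordered on suspicion has no role

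*Combined protocol and SAP*

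**What the plan says.** **Progression (13.1.3).** One route to PD is a 25% or greater "increase in the size of the liver and/or spleen as determined by measurement below the respective costal margin". Another is "appearance of new palpable hepatomegaly or splenomegaly that was not previously present". Sections 3.2, 4.4.1 and 13.2 all treat the length below the margin as part of the physical examination. Neither route mentions a second examination or a scan. In the same list, measured nodal PD needs growth in at least two "lymph nodes on two consecutive examinations at least" 2 weeks apart.

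**Partial response (13.1.2).** If the organ was abnormal before treatment, PR needs at least a "50% reduction in abnormal hepatosplenomegaly by CT or physical exam". No precedence is given. The CR rule in 13.1.1 asks for examination and imaging together. PR also requires every other listed criterion, held for at least 4 weeks, and 13.3.1 repeats the 4-week confirmation.

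**Imaging (13.2 and calendar footnote 1).** In patients whose initial scan was abnormal, imaging is routine after even-numbered cycles and "will be done at other times if there is clinical evidence that the patient has had a PR, CR, or progressive disease". Section 13.2 allows CT/MRI or ultrasound. It also says that objective records such as CT scans are kept so that responses can be audited.

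**Recording.** Section 4.4.1 says: "Physical examination should record liver and spleen size as determined by measurement below the respective costal margin". Section 3.2 says the same for baseline. Section 13.2 is weaker: "Physical examination if relevant can record liver and spleen size as determined by measurement below the respective costal margin".

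**Consequence.** Section 4.9.1 lists "Progression of disease during active treatment on study protocol" as a reason for removal from protocol therapy.

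**The concern.** CR/PR is the primary endpoint, and the activity decision turns on small counts: 3 of 10, then 6 of 17. The plan pays for a scan when a response or progression is suspected, then does not say what the scan decides.

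For PR, an examination reading of 50% satisfies the organ criterion even if the scan shows less. For PD, a single examination can satisfy the rule as written, and PD takes the patient off therapy, possibly before a response has developed. A palpated length cannot be re-read afterwards, so a call made on it falls outside the audit that 13.2 provides for.

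The thresholds are also small in absolute terms: 25% of an organ 2, 3 or 4 cm below the margin is 0.5, 0.75 or 1.0 cm.

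**Working it through.** **1. The plan's own figure.** Inputs from 15.2: stop if 0-2 of 10 respond, active if 6 or more of 17, p0 = 0.20, p1 = 0.50. Probability of early termination under p0 = 0.8^10 + 10(0.2)(0.8^9) + 45(0.2²)(0.8^8) = 0.107 + 0.268 + 0.302 = 0.678, which agrees with the stated 0.68. The exact two-stage calculation gives alpha 0.094 and power 0.904. The design arithmetic is sound; the issue is what counts as a response or as progression.

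**2. The rules side by side.**

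| Event | Organ measurement | Repeat or duration | Role of the scan |
|---|---|---|---|
| CR | Examination and imaging | Counts held 4 weeks, then marrow and CT | Required |
| PR | CT or examination | 4 weeks | Optional; no rule if discordant |
| PD, organ | Length below margin, or newly palpable | None stated | None stated |
| PD, measured nodes | Perpendicular products | Two examinations at least 2 weeks apart | Not stated |

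**3. False organ PD, no true change.** Assumptions, none from the documents: true length B, each reading Normal(B, s), independent, baseline also read with error, s = 0.5, 1.0 or 1.5 cm. PD is read if later ≥ 1.25 × baseline reading. The variance of (later − 1.25 × baseline) is s²(1 + 1.5625), so P = Φ(−0.25B / (1.601 s)).

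| B (cm) | s = 0.5 | s = 1.0 | s = 1.5 |
|---|---|---|---|
| 3 | 0.17 | 0.32 | 0.38 |
| 4 | 0.11 | 0.27 | 0.34 |
| 8 | 0.01 | 0.11 | 0.20 |

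Example: B = 3, s = 0.5 gives Φ(−0.75/0.800) = Φ(−0.937) = 0.17. At B = 3, s = 1.5, keeping only positive baseline readings lowers 0.38 to 0.36. If two examinations must agree at 3 cm, simulation gives 0.08, 0.19 and 0.24 (0.22 with positive baselines only).

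Staging precedes each cycle, so cycles 2 to 6 bring five examinations. At 4 cm the chance of at least one false PD reading among five is 0.28, 0.54 and 0.63. The chance of two consecutive ones is 0.09, 0.27 and 0.36.

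**4. False organ PR.** The criterion is later ≤ 0.5 × baseline reading. The variance of (later − 0.5 × baseline) is s²(1 + 0.25). With no true change, P = Φ(−0.5B / (1.118 s)). At 3 cm this is Φ(−2.683), Φ(−1.342) and Φ(−0.894) = 0.004, 0.090 and 0.186. If two examinations must agree, simulation gives 0.0001, 0.014 and 0.050.

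A borderline case is more realistic. At 4 cm with a true 40% reduction, one examination reads 50% or more with probability Φ(−0.4 / (1.118 s)) = 0.24, 0.36 and 0.41; both of two do so with probability 0.08, 0.16 and 0.20. These are probabilities for the organ criterion only, not for PR.

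**5. Sensitivity of the decision.** The rates here are illustrative and are not derived from steps 3 and 4. If a fraction f of non-responders is counted as responding, the response probability under p0 is 0.20 + 0.80f: f = 0.02 gives 0.216 and alpha 0.127; f = 0.05 gives 0.24 and alpha 0.185. If 5% or 10% of responders are lost, p1 becomes 0.475 or 0.45 and power 0.867 or 0.820.

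**The case against.** The strongest reply is that palpation error alone cannot make a responder. PR needs neutrophils, platelets and hemoglobin to qualify, plus the hairy cell count where it was abnormal, all for 4 weeks. This stands. A reader might infer that examiner error can create a response; the text supports only that it can decide the organ criterion in a patient who meets everything else.

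A reader might also infer that a CT is ordered whenever PR or PD is suspected. Section 13.2 limits this to patients with an abnormal initial scan and allows ultrasound. The limit leaves its own gap: after a normal initial scan, a newly palpable organ is PD and that provision triggers no imaging.

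The illustration depends on organ size as well as on examiner SD, and the documents give neither. They also do not say how many patients have a palpable organ; symptomatic splenomegaly is one of five alternative indications for entry. At 8 cm with an SD of 0.5 cm the problem nearly vanishes.

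The contrast with nodes is partial: new palpable nodes and the circulating-cell criterion also lack a stated repeat. That one examination suffices for organ PD is inferred from silence, as is the view that a scan cannot overturn it.

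Section 4.10, which allows assessments at NIH or elsewhere, concerns patients off treatment. It does not show that on-treatment PD is judged by varying outside examiners.

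Finally, 4.4.1 already says the measurement should be recorded before each cycle, so the weaker wording in 13.2 is a small matter.

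**Conclusion.** The point holds in a limited form. As written, a favourable palpation can satisfy the organ part of PR against a scan that does not, and organ PD can be called on a palpated length with no stated repeat while the scan ordered on suspicion has no stated role. No other section resolves either gap.

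PD is the stronger limb: about 0.17 to 0.38 per examination at 3 cm, 0.11 to 0.34 at 4 cm and 0.01 to 0.20 at 8 cm for an unchanged organ. The PR limb is weaker: 0.004 to 0.19 at one examination at 3 cm and 0.0001 to 0.05 if two must agree, before the remaining PR criteria are applied. All these figures rest on an assumed SD of 0.5 to 1.5 cm with independent errors.

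A reader might go further and conclude that the trial's activity decision is unreliable. The documents do not support that: the number of affected patients is unknown, and one patient at the 6-of-17 boundary would matter under any criterion.

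**What to change.** **Section 13.1.2.** Fix one method per patient at baseline for liver and spleen and use it throughout. Where the baseline scan showed organomegaly, let the imaging already ordered by 13.2 take precedence over palpation. Name the imaging dimension to which the 50% applies, because a length below the margin does not carry over to a scan. The cost is wording, and some PRs supported by palpation alone would no longer count.

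**Section 13.1.3.** Reconcile it with 13.2, calendar footnote 1 and the nodal repeat rule: state which measurement decides organ PD and what happens when examination and scan disagree, including after a normal initial scan. Because PD ends protocol therapy, the rule itself is for the sponsor and investigator to settle, and none is proposed here. When weighing a repeat, note that on-treatment staging is pre-cycle and about 28 days apart, so a 2-week repeat would need an added visit and waiting for the next staging would take about 4 weeks.

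**Section 13.2.** Make the recording of liver and spleen size agree with 3.2 and 4.4.1. This costs nothing beyond the edit.
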